2.2 Secondary Objective(s)

1. Percentage of MDS participants with complete remission (CR) and complete remission with incomplete marrow recovery (CRi)
2. Percentage of AML participants with complete remission (CR) and complete remission with incomplete marrow recovery (CRi)
- 3.

This will be calculated based on current International Working Group (IWG) criteria. CR is defined as absolute neutrophil count $> 1000/\text{microliter (mCL)}$, platelets $> 100k/\text{mCL}$, red cell transfusion independence, and bone marrow with $< 5\%$ blasts. CRi is defined as bone marrow with less than 5% blasts, and absolute neutrophils of $\leq 10000/\text{mCL}$ or platelets $\leq 100k/\text{mCL}$

4. Event-free survival (EFS)

EFS will be defined as the number of days from randomization to the date of progressive disease, relapse from CR or CRi, treatment failure or death from any cause.

5. Complete remission or complete remission with partial hematologic recovery rate (CR+CRh)

A response of CRh is defined as Bone marrow with $< 5\%$ blasts, peripheral blood neutrophil count $> 0.5 * 10^3/\text{mCL}$ and peripheral blood platelet count $> 0.5 * 10^5/\text{mCL}$.

6. Post baseline transfusion independence rate

Transfusion Independence is defined as a period of 56 days with no transfusion between first dose of study drug and the last dose of study drug + 30 days. The rate of conversion for red blood cells (RBC) and platelets is defined as percentage of participants being post-baseline transfusion independent from baseline transfusion dependence.

7. Rate of Hospitalization

Defined as hospitalization for complication related to myeloid malignancy or treatment. Initial admission for diagnosis or initiation of therapy will not be considered an event.

8. Infection rate requiring hospitalization

Defined as being hospitalized due to an infection or sepsis.

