11.0 MEASUREMENT OF EFFECT

Responses for CR, PR and HI will be described per IWG criteria for MDS and MPN^{23,24}. For AML will use ELN response criteria. Additionally, in order to focus the most objective outcomes, additional MDS/MPN response criteria of spleen response and symptoms response will not be part of the measurement of effect of response, although will be collected as available for descriptive purposes.

Table 2: Criteria for Hematologic Improvement (HI)

Hematologic Improvement (HI)	Response Criteria (Must last at least 8 weeks)
Erythroid Response (pretreatment < 11g/dL)	
 • Hgb increase by \geq g/dL • Relevant reduction of units of RBC transfusions by an absolute number of at least 4 RBC transfusions/8 weeks compared with the pretreatment transfusion number in the previous 8 weeks.
Platelet response (pretreatment, < $100 \times 10^9/L$)	
 • Absolute increase of $\geq 30 \times 10^9/L$ for patients with $> 20 \times 10^9/L$ platelets • Increase from $< 20 \times 10^9/L$ to $> 20 \times 10^9/L$ and by at least 100%
Neutrophil response (pretreatment < $1.0 \times 10^9/L$)	
 • At least 100% increase and an absolute increase $> 0.5 \times 10^9/L$

*Pretreatment values should not be influenced by transfusion, if they are considered transfusion dependent

Table 3: Response criteria for patients with primary diagnosis of MDS²³

Category	Response Criteria (response must last at least 4 weeks)
Complete Remission	
 • Bone marrow: $\leq 5\%$ myeloblasts with normal maturation of all cell lines. (Note persistence of dysplasia) • Peripheral Blood 
 ◦ Hgb $\geq 11\text{g/dL}$ ◦ Platelets $\geq 100 \times 10^9/\text{L}$ ◦ Neutrophils $\geq 1.0 \times 10^9/\text{L}$ ◦ Blasts 0%
Partial Remission	
 • All CR criteria if abnormal before treatment except: 
 ◦ Bone marrow blasts decreased by $\geq 50\%$ over pretreatment but still $> 5\%$ ◦ Cellularity and morphology no relevant
Marrow CR	
 • Bone marrow: $\leq 5\%$ myeloblasts and decrease by $\geq 50\%$ over pretreatment • Peripheral blood: if HI responses, should be noted in addition to marrow CR. (for this protocol, marrow CR absent HI is NOT considered a response)

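### Sections 2.2 and 11 define CR differently for MDS and AML, and CRi differently for AML, and nothing says which governs

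*Combined protocol and SAP*

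**What the plan says.** Section 2.2 lists the percentages of MDS and of AML participants with CR and CRi as secondary objectives, and says of both: "This will be calculated based on current International Working Group (IWG) criteria". One definition then serves both diseases.

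- CR: neutrophils above 1000/mcL, platelets above 100k/mcL, "red cell transfusion independence, and bone marrow with" fewer than 5% blasts.
- CRi: "CRi is defined as bone marrow with less than 5% blasts, and absolute neutrophils of" at most 10000/mcL, or platelets at most 100k/mcL.
- CRh has its own definition, beginning "A response of CRh is defined as Bone marrow with".
- EFS counts "relapse from CR or CRi, treatment failure or death from any cause", along with progression.

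Section 11 works by disease.

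- MDS (Table 3, IWG). The column header reads "Response Criteria (response must last at least 4 weeks". CR needs at most 5% "myeloblasts with normal maturation of all cell lines. (Note persistence of dysplasia", haemoglobin at least 11 g/dL, platelets at least 100, neutrophils at least 1.0 (both ×10⁹/L) and no blood blasts. There is no CRi row. Marrow CR without haematologic improvement (HI) is expressly not a response. The relapse row covers CR and PR only.
- AML: "For AML will use ELN response criteria". Table 5 CR needs marrow blasts below 5%, no circulating blasts, no Auer rods, no extramedullary disease, and the same neutrophil and platelet limits. CRi is CR apart from residual neutropenia or thrombocytopenia. The relapse row includes relapse after CRi.

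Section 13 bases the MDS and AML targets on the precision of the CR rate and does not name a definition.

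**The concern.** Both texts are operative and both are directive. Section 2.2 says how the rates will be calculated, and Section 11 says how response will be measured. Where they differ, the same patient can be counted as CR or not depending on which page the analyst opens.

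This matters because the expansion phase exists largely to estimate efficacy. Section 13 justifies 32 MDS and 38 AML patients by the standard error of the CR rate, and the rationale for cohort expansion says the data will guide later sample sizes. A CR rate without a fixed definition is a weak basis for either use. Some responses are already known: the same rationale reports 7 of 11 AML patients responding. A definition chosen late could therefore be chosen with results in view.

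**Working it through.** **1. The plan's own figures.** Section 13 expects CR rates of 36% (MDS, n = 32) and 38% (AML, n = 38), with standard errors of at most 9% and 8%. With SE = √[p(1−p)/n]:

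- MDS: √(0.36 × 0.64 / 32) = 8.5%
- AML: √(0.38 × 0.62 / 38) = 7.9%

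Both reproduce at the planned rates. Settling the CR definition does not alter n or this formula.

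**2. CR compared on test profiles.** All have neutrophils 1500/mcL and platelets 150k/mcL, and meet every condition not mentioned. The 10000 limit is read as 1000, so that a likely typing error does not drive the result.

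| Profile | Section 2.2 | Section 11 |
|---|---|---|
| MDS, Hgb 9, untransfused, marrow blasts 3% | CR | not CR (Table 3: Hgb) |
| MDS, Hgb 11.5, untransfused, marrow blasts exactly 5% | not CR | CR (Table 3) |
| AML, marrow blasts 3%, still red-cell transfused | neither CR nor CRi | CR (Table 5) |
| AML, untransfused, marrow blasts 3%, blood blasts 1% | CR | not CR (Table 5: blood blasts) |

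An MDS response lasting only 2 weeks is also CR under Section 2.2 but not under Table 3.

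**3. CRi in AML.** A patient with marrow blasts 3%, neutrophils 800/mcL and 1% circulating blasts is CRi under Section 2.2. Table 5 CRi still requires no circulating blasts, so the patient is not CRi there.

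**4. CRi in MDS.** Only Section 2.2 defines it. A patient with marrow blasts 3%, platelets 60k/mcL and no HI is CRi under Section 2.2. Under Table 3 the same patient is at best marrow CR without HI, which does not count as a response.

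**5. The limit as printed.** At 10000, any Section 2.2 CR patient with neutrophils above 1000 and up to 10000/mcL also meets CRi. The first and fourth profiles become both CR and CRi. The third becomes CRi under Section 2.2 while remaining CR under Table 5.

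**6. Sensitivity.** One reclassified patient moves the CR rate by 1/32 = 3.1 points (MDS) or 1/38 = 2.6 points (AML). One planned standard error corresponds to 0.085 × 32 = 2.7 patients in MDS and 0.079 × 38 = 3.0 in AML. These figures are arithmetic per patient; they do not predict how many patients would change category.

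**The case against.** The best defence is that Section 2.2 is only a loose summary. For MDS both sections cite IWG criteria, and Table 3 reproduces those criteria under the heading on measurement of effect, so Table 3 would naturally govern. For AML, Section 11 says outright that ELN will be used. This has force as a guess at intent, and it points to the right repair. It does not settle the matter. Section 2.2 states its own thresholds as the basis of calculation for both diseases, and Section 11 cannot supply every listed endpoint, since it has no MDS CRi and no CRh.

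Four further points limit the concern, and they stand.

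- In MDS, the direction of CR under Table 3 but not under Section 2.2 arises mainly at boundary values, such as marrow blasts of exactly 5% or counts exactly at the limit. A patient with haemoglobin of at least 11 g/dL who is still transfused would also qualify on the CR row, but Table 3 lists transfusion dependence under relapse and progression.
- The AML profile with circulating blasts needs Section 2.2 to be read as exhaustive. The still-transfused AML patient is the firmer example.
- MDS CRi is not defined twice. It is defined once, in tension with the marrow CR rule. CRh is likewise defined once, without conflict.
- The 10000 limit is probably a slip for 1000, and correcting it leaves the other differences in place.

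**Conclusion.** The conflict is real and should be corrected. As written, the CR rate in both diseases and the CRi rate in AML have two incompatible definitions, MDS CRi is not tied to Section 11, and the printed neutrophil limit makes CR and CRi overlap for most CR patients. The clearest cases are untransfused MDS with haemoglobin below 11 g/dL and AML in remission with continuing red-cell transfusion; neither rests on a boundary value or on the 10000 limit.

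The size is bounded only per patient, at 3.1 points in MDS and 2.6 in AML. The documents do not give the number affected or the net direction. The primary endpoint, the sample sizes and the standard errors do not change.

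Two stronger readings are tempting. A reader might assume some number of reclassified patients and express the shift as a share of the gap to the single-agent CR rates in Section 13 (16% in MDS, 17.9% in AML). The count would be invented, and Section 13 sets only a precision target, with no test of CR against those rates. Entry to the expansion phase depends on dose reductions. A reader might also infer that EFS is broadly compromised. Table 5 already defines AML relapse after CRi, so the gap is confined to relapse from MDS CRi, which the Table 3 relapse row omits. How many such events Table 3 progression would capture cannot be told from the documents.

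**What to change.** - State in Section 2.2 that CR is assessed by Section 11 (Table 3 for MDS, Table 5 for AML) and AML CRi by Table 5.
- Delete the conflicting CR and CRi text from Section 2.2, including the 10000 limit. Keep the CRh definition.
- Keep MDS CRi as an endpoint with one explicit definition, mutually exclusive with CR and consistent with the rule that marrow CR without HI is not a response. Replacing it with marrow CR plus HI is not needed and would change a named secondary endpoint mid-trial.
- Add relapse from MDS CRi to the Table 3 relapse row so that it matches the EFS definition.
- Apply the rule to all patients, including those already assessed, and disclose that it was settled after early response data were seen. The reported 7 of 11 is an overall response rate, with no split into CR and CRi.

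The cost is an amendment to wording and some reclassification. Blood counts are largely to hand, since the Section 10 calendar already treats all collected CBCs as efficacy data. Marrow maturation, Auer rods, extramedullary disease and response duration must also be retrieved. CR rates may move in either direction.

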4.1 Inclusion Criteria

Subjects must meet all of the following inclusion criteria to be eligible for enrollment:

1. Patient must have a diagnosis of MDS, AML, CMML or MDS/MPN with a histopathologic diagnosis confirmed by hematopathology review

AND

2. Indication for therapy with potential sensitivity to HMA therapy, defined as prior published evidence of response to HMA.

AND

3. Patients must be 18 years of age or older

AND

4. Patients must have an ECOG performance status of ≤ 3

AND

5. Patients must have adequate end organ function defined as.

- AST and ALT $< 4 \times$ the upper limit of normal (ULN)
- Bilirubin $\leq 2 \times$ the ULN. If elevated bilirubin is due to impaired conjugation (e.g. Gilbert's disease or concomitant medication) or disease related hemolysis, then direct bilirubin $\leq 1.5 \times$ the ULN.
- As decitabine and venetoclax have little renal metabolism, and have proven safety even in dialysis patients, renal function with a creatinine clearance ≥ 30 mL/min or on dialysis is allowed.¹⁸

AND

6. Subjects must have the ability to understand and the willingness to sign a written informed consent document and complete study related procedures.

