Stable Disease	
 • Failure to achieve at least PR, but no evidence of progression for > 8 weeks
Failure	
 • Death during treatment or disease progression characterized by worsening of cytopenias, increase in percentage of bone marrow blasts, or progression to a more advanced MDS subtype than pretreatment
Relapse after CR or PR	
 • At least one of the following: 
 ◦ Return to pretreatment bone marrow blast percentage ◦ Decrement of $\geq 50\%$ from maximum remission/response levels in granulocytes or platelets ◦ Reduction in Hgb concentration by $\geq 1.5\text{g/dL}$ or transfusion dependence
Cytogenetic response	
 • Complete: Disappearance of the chromosomal abnormality without appearance of the new ones • Partial: at least 50% reduction of the chromosomal abnormality
Disease Progression	
 • For patients with: 
 ◦ Less than 5% blasts: $\geq 50\%$ increase to $> 5\%$ blasts ◦ 5%-10% blasts: $\geq 50\%$ increase to $> 10\%$ blasts ◦ 10-20% blasts: $\geq 50\%$ increase to $> 20\%$ blasts • Any of the following: 
 ◦ At least 50% decrement from maximum remission/response in granulocytes or platelets

- Reduction in hgb by $\geq 2\text{g/dL}$
- Transfusion dependence

In general, all reductions in to define progression counts must not be attributable to treatment. If treatment causes transient reductions in counts, response should be considered durable through therapy. Other concomitant causes such as infection or bleeding need to be considered to ensure there is not concomitant causes.

Table 4: Response Criteria for patient with a primary diagnosis of MDS/MPN²⁴

Category	Response Criteria (response must last at least 4 weeks)

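### Section 2.2 defines CRh, and CRi for MDS, without any baseline or change condition, so unchanged low-blast disease can be counted as a response

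*Combined protocol and SAP*

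**What the plan says.** Section 2.2, item 5, gives the only definition of CRh in the protocol: "A response of CRh is defined as Bone marrow with $< 5\%$ blasts", with a neutrophil count above 0.5 x 10^3/mCL "and peripheral blood platelet count" above 0.5 x 10^5/mCL. The item names no disease, so it covers every enrolled diagnosis.

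The CRi rule in section 2.2, under the MDS and AML response items, reads: "CRi is defined as bone marrow with less than 5% blasts, and absolute neutrophils of" at most 10000/mCL (as printed), or platelets at most 100k/mCL. Neither rule refers to the pretreatment value.

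On who may enter, section 4.1 says: "Patient must have a diagnosis of MDS, AML, CMML or MDS/MPN with a histopathologic diagnosis confirmed by hematopathology review". It sets no minimum blast percentage and no MDS risk category. Two other places provide for low-blast patients. The progression rows of Tables 3 and 4 have a branch headed "Less than 5% blasts", and the G-CSF text in section 6.2 addresses patients below 5% marrow blasts during induction.

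Section 11 takes a stricter line for MDS. Table 3 defines marrow CR as at most 5% "myeloblasts and decrease by $\geq 50\%$ over pretreatment", and adds that marrow CR without hematologic improvement (HI) does not count as a response in this protocol.

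**The concern.** A response category should record a change brought about during treatment. A category built only from absolute values does so only if patients could not have met those values at entry. In AML the diagnosis normally secures this. In MDS, CMML and MDS/MPN it does not, and the eligibility criteria do not supply the missing condition.

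At stake are the secondary CR+CRh rate and the MDS CRi rate. In a single-arm study no control group would show the inflation. The missing condition can only add responders and never remove them, so the error runs in one direction. The same labels feed other analyses: event-free survival counts relapse from CRi, and the scientific correlate relates DNMT1 depletion to clinical response.

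**Working it through.** **1. The plan's own figure.** The nearest stated number is the standard error for the MDS CR rate in section 13.0: no more than 9% with 32 patients. SE = sqrt(p(1-p)/n). At p = 0.36, sqrt(0.36 x 0.64/32) = 8.5%. At the worst case p = 0.5, sqrt(0.25/32) = 8.8%. The figure reproduces. It describes sampling error in the CR rate and does not address classification.

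**2. One patient, two rulebooks.** Take a hypothetical MDS patient with 3% marrow blasts, ANC 0.9 x 10^9/L (900/mCL) and platelets 70 x 10^9/L (70,000/mCL), with all values the same at entry and at week 12.

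| Rule | Condition | Result |
|---|---|---|
| 2.2 CRh | blasts <5%; ANC >500; platelets >50,000 | met at entry and at week 12 |
| 2.2 CRi | blasts <5%; ANC <=10000 or platelets <=100k | met at entry and at week 12 |
| Table 3 CR | ANC >=1.0 and platelets >=100 x 10^9/L, among others | not met |
| Table 3 marrow CR | blasts <=5% and a fall of >=50% | not met, fall is 0% |
| Table 2 HI | improvement in counts | not met |
| Table 3 Stable Disease | less than PR, no progression for >8 weeks | met |

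The same unchanged patient is CRh and CRi under section 2.2 and Stable Disease under Table 3.

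**3. Does another passage repair it?**
- Section 2.2 refers CR and CRi to IWG criteria, but the IWG-based Table 3 has no CRi or CRh category, and Table 4 has neither.
- Table 5 defines CRi for AML only and does not define CRh.
- The requirement in Tables 3 and 4 that a response last at least 4 weeks is satisfied by disease that does not change.

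For MDS, section 2.2 is therefore the only definition of either category. For CMML and MDS/MPN it is the only definition of CRh.

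**4. Size, as illustration.** Let f be the share of a disease group that meets the definition at entry and stays unchanged, and p the true rate in the others. Then:

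apparent rate = f + (1-f)p, and excess = f + (1-f)p - p = f(1-p).

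Both f and p are assumptions. The two values of p only span a range.

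| f | p = 0.16: apparent (excess) | p = 0.36: apparent (excess) |
|---|---|---|
| 10% | 24.4% (8.4 points) | 42.4% (6.4 points) |
| 20% | 32.8% (16.8 points) | 48.8% (12.8 points) |
| 30% | 41.2% (25.2 points) | 55.2% (19.2 points) |

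At f = 0 there is no bias.

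**5. Precision if low-blast patients are set aside.** With n = 32(1-f) and worst case p = 0.5, the SE is sqrt(0.25/28.8) = 9.3% at f = 10%, sqrt(0.25/25.6) = 9.9% at f = 20%, and sqrt(0.25/22.4) = 10.6% at f = 30%. Holding 9% in the worst case needs 31 patients (0.25/0.0081 = 30.9).

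**The case against.** The strongest reply has four parts.

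*The endpoint is secondary and descriptive.* No test, target or go/no-go rule uses CRh or CRi, and section 13.0 sizes the expansion on the CR rate alone. This stands, and it sets the severity.

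*Low-blast entry may be rare.* The MDS rationale in section 1.3.4 concerns high-risk disease, and the low-blast branch of Table 3 may be carried over from published criteria. This also stands as to frequency. It does not show that such patients are excluded: section 4.1 admits them and section 6.2 provides for them.

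*The protocol's intent is visible in Table 3.* It is, for MDS. But Table 3 never mentions CRh or CRi, so an analyst following section 2.2 would not be bound by it.

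*CRh is not decided by blasts alone.* Correct. A reader might infer that every patient below 5% is a responder at entry, but one below either count floor does not meet CRh. Nor does the CRi limb reach CMML through section 2.2, since the items it serves name MDS and AML participants; for CMML the point rests on CRh.

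A reader might also infer that about eight of 32 MDS patients would lift a regimen no better than single-agent HMA (16%) to the 36% expected of the combination, since 0.16 + 0.84 x 8/32 = 37%. The documents do not support that reading. The 16% and 36% are CR rates, CR+CRh is a broader endpoint that would exceed a CR benchmark without any misclassification, and the eight patients are an assumption.

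**Conclusion.** The concern holds as a defect in the definition. As written, section 2.2 can count unchanged disease as CRh in MDS, CMML and MDS/MPN, and as CRi in MDS, in contradiction to how Table 3 would class the same MDS patient. The bias in the CR+CRh rate and the MDS CRi rate is upward only. Its size is f(1-p) and cannot be computed from the documents, because they give no baseline distribution of blasts or counts. The 6 to 25 points above rest on assumed values of f from 10% to 30% and should not be set against the plan's CR benchmarks.

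It would go too far to say that the expansion's sizing is compromised. The primary endpoint, the Simon design and the CR-based standard-error calculation do not use these definitions. Severity: should-fix.

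**What to change.** Amend section 2.2 before response rates are analysed:

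- CRi and CRh can be assigned only to patients with baseline marrow blasts of at least 5%. For MDS, CMML and MDS/MPN, also require the fall of at least 50% from pretreatment that Table 3 already uses for marrow CR.
- Patients below 5% at entry can respond only through CR, with at least one CR blood-count criterion abnormal at baseline, or through HI. The second condition is needed because the section 2.2 CR definition also carries no baseline requirement.
- Keep all patients of the disease group in the denominator. Report the rate among patients with at least 5% baseline blasts as a supporting analysis with its own standard error, which may exceed 9% (step 5).
- Reconcile the printed CRi neutrophil limit of 10000/mCL with the 1000/mCL used for CR in section 2.2 and for CRi in Table 5. As printed, almost any neutrophil count satisfies it.

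Cost: a short change to the definitions. Section 9.1 already provides for a baseline marrow in all patients, so no new data are needed. The downside is somewhat lower reported CR+CRh and CRi rates.

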3.0 STUDY DESIGN

This will be a single arm, open label pilot study of weekly dosing of subcutaneous decitabine and venetoclax

Patients will be treated for a minimum of 12 weeks in the absence of clear evidence of progressive disease. Patients who have any response will be permitted to continue treatment until relapse or progression of disease. Primary endpoint will be the percentage of patients who will require dose interruptions due to cytopenias. Secondary endpoints will include assessment of response rates, transfusion dependence, rate of infections and hospitalizations.

Exploratory endpoints will include assessment of the ability of weekly low doses of Dec and Ven to cause DNMT1 depletion on bone marrow samples.

